7.3 LOST TO FOLLOW-UP

A subject will be considered lost to follow-up if he or she fails to return for ≥ 3 scheduled visits and is unable to be contacted by the study staff.

The following actions must be taken if a subject fails to return to clinic for a required study visit:

- Site will attempt to contact the subject and reschedule the missed visit and advise subject on importance of maintaining assigned visit schedule
- Before a subject is deemed lost to follow-up, study staff will make three documented attempts to contact the subject. Should the subject continue to be unreachable, he or she will be considered to have withdrawn from the study.

8 STUDY ASSESSMENTS AND PROCEDURES

8.1 EFFICACY ASSESSMENTS

8.1.1 CNS SURVEILLANCE:

Patients will have surveillance brain MRIs at week 3 (± 4 days), 3 months (13 weeks ± 7 days), then every 3 months (± 14 days). CNS disease status will be graded (complete response, partial response, stable disease, progressive disease) per the modified RANO-BM criteria (Lin, et al *The lancet oncology* 16.6 (2015): e270-e278). Per modified RANO-BM, brain lesions with a unidimensional diameter of ≥ 5 mm are evaluable as measurable lesions.

	Complete Response	Partial Response	Stable Disease	Progressive Disease
Target lesion	None	$\geq 30\%$ decrease in sum longest distance relative to baseline	$<30\%$ decrease relative to baseline but $<20\%$ increase in sum longest	$\geq 20\%$ increase in sum longest distance relative to nadir*

	Complete Response	Partial Response	Stable Disease	Progressive Disease
			distance relative to nadir	
Non-target lesions	None	Stable or improved	Stable or improved	Unequivocal progressive disease*
New lesion (s) [†]	None	None	None	Present*
Corticosteroids	None	Stable or decreased	Stable or decreased	Not applicable [‡]
Clinical status	Stable or improved	Stable or improved	Stable or improved	Worse*
Requirements for response	All	All	All	Any

* Progression occurs when this criterion is met.

† A new lesion is one that was not present on prior scans and is visible in minimum two projections. If a new lesion is equivocal, for example because of its small size, continued therapy can be considered, and follow-up assessment will clarify if the new lesion is new disease. If repeat scans confirm there is definitely a new lesion, progression should be declared using the date of the initial scan showing the new lesion. For immunotherapy-based approaches, new lesions alone do not define progression.

‡ Increase in corticosteroids alone will not be taken into account in determining progression in the absence of persistent clinical deterioration.

TARGET LESIONS

COMPLETE RESPONSE:

Disappearance of all CNS target lesions sustained for at least 4 weeks; with no new lesions, no use of corticosteroids, and patient is stable or improved clinically.

PARTIAL RESPONSE:

At least a 30% decrease in the sum longest diameter of CNS target lesions, taking as reference the baseline sum longest diameter sustained for at least 4 weeks; no new lesions; stable to decreased corticosteroid dose; stable or improved clinically.

PROGRESSIVE DISEASE:

At least a 20% increase in the sum longest diameter of CNS target lesions, taking as reference the smallest sum on study (this includes the baseline sum if that is the smallest on study). In addition to the relative increase of 20%, at least one lesion must increase by an absolute value of 5 mm or more to be considered progression.

STABLE DISEASE:

Neither sufficient shrinkage to qualify for partial response nor sufficient increase to qualify for progressive disease, taking as reference the smallest sum longest diameter while on study.

NON-TARGET LESIONS

Non-target lesions should be assessed qualitatively at each of the imaging time points specified in the protocol.

COMPLETE RESPONSE:

Requires all of the following: disappearance of all enhancing CNS non-target lesions, no new CNS lesions.

NON-COMPLETE RESPONSE OR NON-PROGRESSIVE DISEASE:

Persistence of one or more non-target CNS lesion or lesions.

PROGRESSIVE DISEASE:

Any of the following: unequivocal progression of existing enhancing non-target CNS lesions, new lesion(s) (except while on immunotherapy-based treatment), or unequivocal progression of existing tumor-related non-enhancing (T2/FLAIR) CNS lesions.

8.1.2 EXTRACRANIAL SURVEILLANCE

Patients will have surveillance imaging of the body at 3 months (13 weeks \pm 7 days) and then every 3 months (\pm 14 days) for 2 years or as required for standard of care by the investigator. At the discretion of the investigator, the patient may have a computed tomography (CT) scan of the chest/abdomen, with or without the pelvis OR a positron emission tomography-computed tomography (PET/CT) scan. Extracranial disease status will be graded per standard RECIST 1.1 criteria (Eisenhauer et al. "New response evaluation criteria in solid tumours: revised RECIST guideline (version 1.1)." *European journal of cancer* 45.2 (2009): 228-247.)

8.1.3 QUALITY OF LIFE (QOL) ASSESSMENTS.

QOL will be assessed using the EORTC QLQ-C30 and BN20 brain-specific questionnaire. The EORTC QLQ-C30 is one of the most frequently used questionnaires in cancer patients, and the BN20 is a supplemental questionnaire specifically developed for use with the QLQ-C30 in patients with brain cancer. Both tools have robust psychometric properties resulting from rigorous testing, development, and external validity, and have been used in numerous of oncology trials (Efficace 2002). Specific to PCI, the QLQ-C30 and BN20 have been used in the RTOG PCI trials (RTOG 0212 and 0214) (Gondi 2013), the EORTC 08993-22993 PCI trial (Slotman 2007), and the Intergroup PCI trial (Le Pechoux 2011). The questionnaires are translated and validated in over 80 languages. Use of the questionnaires requires no monetary charge in the non-commercial setting. Together, the questionnaires typically take under 5 minutes to complete, and collection is planned at baseline and with each planned clinical surveillance visit (with the exception of Day 8).

8.2 SAFETY AND OTHER ASSESSMENTS

Adverse events will be assessed at scheduled clinical follow up visits or any intervening time when new adverse events are reported by enrolled patients.

8.3 ADVERSE EVENTS AND SERIOUS ADVERSE EVENTS

8.3.1 DEFINITION OF ADVERSE EVENTS (AE)

Adverse event means untoward or unfavorable medical occurrence considered to be related to a study intervention or treatment in humans.

8.3.2 DEFINITION OF SERIOUS ADVERSE EVENTS (SAE)

Serious adverse event or serious suspected adverse reaction. An AE or suspected adverse reaction is considered “serious” if, in the view of either the investigator or sponsor, it results in any of the following outcomes: death, a life-threatening adverse event, inpatient hospitalization or prolongation of existing hospitalization, a persistent or significant incapacity or substantial disruption of the ability to conduct normal life functions, or a congenital anomaly/birth defect. Important medical events that may not result in death, be life-threatening, or require hospitalization may be considered serious when, based upon appropriate medical judgment, they may jeopardize the patient or subject and may require medical or surgical intervention to prevent one of the outcomes listed in this definition. Examples of such medical events include allergic bronchospasm requiring intensive treatment in an emergency room or at home, blood dyscrasias or convulsions that do not result in inpatient hospitalization, or the development of drug dependency or drug abuse.

8.3.3 CLASSIFICATION OF AN ADVERSE EVENT

8.3.3.1 SEVERITY OF EVENT

The adverse event severity grading scale for the NCI CTCAE (v4.03) will be used for assessing adverse event severity. The following table will be used for assessing severity for adverse events that are not specifically listed in the NCI CTCAE (v4.03).

Grade	Severity
1	Mild; asymptomatic or mild symptoms; clinical or diagnostic observations only; or intervention not indicated

Grade	Severity
2	Moderate; minimal, local, or non-invasive intervention indicated; or limiting age-appropriate instrumental activities of daily living ^a
3	Severe or medically significant, but not immediately life-threatening; hospitalization or prolongation of hospitalization indicated; disabling; or limiting self-care activities of daily living ^{b,c}
4	Life-threatening consequences or urgent intervention indicated
5	Death related to adverse event

NCI CTCAE National Cancer Institute Common Terminology Criteria for Adverse Events. Note: Based on the most recent version of NCI CTCAE (v4.03), which can be found at: http://ctep.cancer.gov/protocolDevelopment/electronic_applications/ctc.htm

^a Instrumental activities of daily living refer to preparing meals, shopping for groceries or clothes, using the telephone, managing money, etc.

^b Examples of self-care activities of daily living include bathing, dressing and undressing, feeding oneself, using the toilet, and taking medications, as performed by patients who are not bedridden.

^c If an event is assessed as a "significant medical event," it must be reported as a serious adverse event.

8.3.3.2 RELATIONSHIP TO STUDY INTERVENTION

Only adverse events directly related to study treatment or procedures will be recorded. All serious adverse events, both related and not related, will be reported per section 8.3.6. If there is any doubt as to whether a clinical observation is related or not related to the study treatment or procedures, the event should be reported as related.

To help assess, the following guidelines will be used.

- **Related** – The AE is known to occur with the study procedures, there is a reasonable possibility that a study procedure caused the AE, or there is a temporal relationship between the study procedure and event. Reasonable possibility means that there is evidence to suggest a causal relationship between the study procedures and the AE.
- **Not Related** – There is not a reasonable possibility that the study procedure caused the event, there is no temporal relationship between the study procedure and event onset, or an alternate etiology has been established.

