2.3 RISK/BENEFIT ASSESSMENT

2.3.1 KNOWN POTENTIAL RISKS

This study involves the treatment of patients with BM from ALK+ NSCLC with brigatinib alone and close clinical and MRI surveillance (delaying CNS RT until potential CNS progression, if that were to occur in the future). The primary risk is the potential for higher rates of CNS progression, which is the focus of the trial and the primary endpoint of the study. BM can cause neurologic symptoms, anxiety, require treatments, and may be potentially life threatening in some cases. For this reason, the study involves close clinical follow up and MRI surveillance, to allow early interventions if CNS progression were to occur in patients treated on the trial.

Additional risks are related to the side effect profile of the drug brigatinib. Brigatinib is an FDA approved standard therapy in the first and subsequent lines for patients with metastatic ALK+ NSCLC according to the contemporary NCCN non-small cell lung cancer guidelines. The side effect profile of brigatinib is detailed in subsequent sections of the protocol. In patients who develop CNS progression and require CNS RT, the standard risks associated with CNS RT including fatigue, hair loss, headaches, nausea, and small risks of seizure, radiation necrosis, and focal neurologic deficits apply. It is important to note that CNS RT is considered the gold standard treatment for brain metastases, endorsed by the contemporary NCCN CNS tumor guidelines (v2.2019) and the above risks are considered standard side effects with radiation in this setting that are applicable to patients treated on or off protocol.

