9.4.4 SAFETY ANALYSES

Safety will be measured via the CTCAE Version 4.03 criteria and the rate and type of adverse event (AE) will be compared to historical controls and assessed for any increased risk. Listings will be produced of all study-related AEs, which will be reviewed by the study PI. Additionally, any serious adverse event (SAE) will be reported within 24 hours to the study PI who will investigate the attribution of the SAE to the experimental treatment and only continue the study if the experimental treatment is considered safe.

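### Non-serious adverse events are recorded only if judged related, so neurologic events attributed to the brain metastases can drop out of the AE data, and the historical comparison states no attribution basis

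*Combined protocol and SAP*

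**What the plan says.** Relatedness is built into the AE definition in Section 8.3.1: "Adverse event means untoward or unfavorable medical occurrence considered to be related to a study intervention or treatment in humans". Section 8.3.3.2 turns this into a recording rule: "Only adverse events directly related to study treatment or procedures will be recorded". Section 8.3.4 limits case report form capture in the same way, to related AEs plus all SAEs, and the listings in Section 9.4.4 cover study-related AEs only.

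Section 8.3.3.2 also contains provisions that widen capture. For serious events: "All serious adverse events, both related and not related, will be reported per section 8.3.6". For any doubt about attribution: "the event should be reported as related". Among the grounds for Related is a timing criterion, "or there is a temporal relationship between the study procedure and event". Among the grounds for Not Related is "or an alternate etiology has been established".

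The safety analysis in Section 9.4.4 is that "the rate and type of adverse event (AE) will be compared to historical controls and assessed for any increased risk". It names no historical study, rate, attribution basis, margin or test.

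On the risk of the strategy, Section 2.3.1 says: "The primary risk is the potential for higher rates of CNS progression". It also lists neurologic symptoms among the consequences of brain metastases.

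**The concern.** The strategy under test is brigatinib with brain radiation deferred. If deferral does harm, the expected form is neurologic: headache, focal deficit, worsening of existing symptoms. An investigator will often attribute these to the metastases rather than to the drug or to a study procedure. Section 8.3.3.2 does not say whether deferring radiation counts as part of the intervention, and its two tests are worded around study procedures. In an unblinded single-arm trial, attribution is a local judgement, and here that judgement decides whether a non-serious event is recorded at all.

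Baseline symptoms add to the gap. Patients with RTOG/EORTC grade 1 or 2 symptoms are eligible (Section 5.1), and conditions present up to first dose are medical history, not AEs (Section 8.3.4). No explicit rule covers later worsening of those symptoms. The Schedule of Events footnote describes the RTOG/EORTC neurologic grade for baseline only.

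At stake is how far the AE tables can support the short-term safety aim in Section 9.2, and whether the historical comparison in Section 9.4.4 means anything.

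**Working it through.** **Plan's own figure.** The documents give no AE rate, historical rate or safety margin, so there is no safety figure to reproduce. The only design figure is the power of the primary test. With 19 patients and rejection at 16 or more successes, the exact type I error at p = 0.60 is 0.0230 and the power at p = 0.90 is 0.8850, which matches the stated 88.5%. It is not an input here, and the fix does not change it.

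**Tracing one event.** Take a new, non-serious headache in a patient whose metastases have grown.
1. Timing criterion: if its onset is judged temporally linked to a study procedure, it is Related and recorded.
2. Alternative-cause criterion: the metastases were shown on MRI at entry, so another cause can be regarded as established. The event is then Not Related and not recorded.
3. Doubt rule: it brings the event in only if the investigator is unsure. It does nothing when the investigator is confident.

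The two tests overlap, so the same event can satisfy both. Exclusion is permitted but not automatic.

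**Definitions.** Section 8.3.1 requires an AE to be related, and Section 8.3.2 describes a serious event as an AE or suspected adverse reaction with a listed outcome. Section 8.3.3.2 nevertheless requires unrelated SAEs to be reported. Read literally, these do not fit together.

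**Illustration of size (assumed inputs).** Let q be the true proportion of patients with a non-serious neurologic event, f the share judged unrelated, and n = 23 the planned enrolment (Section 9.2), assuming all start brigatinib.
- Expected affected = nq
- Expected recorded = nq(1 − f)
- P(none recorded) = (1 − q(1 − f))^23

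At q = 20%, nq = 23 × 0.20 = 4.6:

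| f | Expected recorded | P(none recorded) |
|---|---|---|
| 0 | 4.6 | 0.80^23 = 0.6% |
| 0.50 | 2.3 | 0.90^23 = 8.9% |
| 0.75 | 1.15 | 0.95^23 = 30.7% |
| 1 | 0 | 100% |

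For q from 10% to 40% with f = 0.50, the recorded rate runs from 5% to 20%. Neither q nor f can be taken from the documents.

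**Direction of the historical comparison.** Suppose the true rate is the same in the trial and in the controls, and let f_h be the share left out of the historical rate. The apparent rate ratio is (1 − f)/(1 − f_h). With f = 0.50:
- all-cause controls (f_h = 0): 0.50/1 = 0.50, so the trial looks safer;
- f_h = 0.25: 0.50/0.75 = 0.67, still safer;
- f_h = 0.75: 0.50/0.25 = 2, so the trial looks worse.

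Without the attribution basis of the controls, the direction is undetermined.

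**The case against.** The strongest reply is that the harm of deferral is measured mainly as efficacy. Section 3 justifies the primary endpoint on grounds of short-term safety as well as efficacy, and Section 2.3.1 identifies CNS progression as that endpoint. In the RANO-BM table (Section 8.1.1), worse clinical status alone is enough for progression. QLQ-C30 and BN20 are collected at every surveillance visit except Day 8, and changes of 10 points or more are analysed. Corticosteroid agent and dose, ECOG status and a physical exam are also recorded. SAE reporting is wider than hospitalised or life-threatening events: Section 8.3.2 includes incapacity and gives convulsions managed without admission as a possible example.

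Much of this stands. A reader might infer that neurologic harm is lost to the trial, or that its safety aim cannot be addressed. The documents do not support that. What remains exposed is milder, non-serious events. The other sources do not close that gap. RANO-BM yields a response category, and an increase in steroids without persistent clinical deterioration does not count as progression. BN20 is a questionnaire, and steroid use is exploratory. None gives a graded AE, and none is named as an input to the Section 9.4.4 comparison.

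A reader might also infer that the comparison is biased toward safety. If the historical rates are all-cause, it is. The plan does not say, so that direction is conditional. Likewise, the f = 1 row above is an extreme: it needs every event to be attributed to disease without doubt.

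Finally, related-only collection is applied consistently and the drug is given at its approved dose, so this is a deliberate choice. Consistency does not resolve the overlapping tests, however, and the question here concerns deferred radiation as well as drug toxicity.

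**Conclusion.** The point holds as a partial gap. Non-serious neurologic events confidently attributed to the metastases can be left out of the AE data, in a trial whose stated main risk is CNS progression. The Section 9.4.4 comparison is uninterpretable as written, because neither its source nor its attribution basis is given. The amount lost cannot be estimated from the documents. Under the assumed 20% event rate in 23 patients, between none and all of the 4.6 expected affected patients would go unrecorded, depending wholly on local attribution. The primary analysis and the sample size are unaffected. This is a cheap improvement worth making.

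**What to change.** 1. In Sections 8.3.3.2 and 8.3.4, record all neurologic AEs regardless of attribution, including worsening of baseline symptoms, with attribution as a separate field.
2. Reconcile the AE definition in Section 8.3.1 with the reporting of unrelated SAEs. Remove the overlap between the Related and Not Related tests, and say whether deferral of radiation is part of the intervention for attribution purposes.
3. Record the RTOG/EORTC neurologic grade at scheduled visits, which already include an exam and AE review.
4. In Section 9.4.4, tabulate all-cause neurologic events beside related AEs. Name the historical source and compare only on the same attribution basis; otherwise report safety descriptively.

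The cost is protocol wording and a few extra eCRF fields, with a modest data-entry burden. No visit is added and no design figure changes.

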8.3.3.3 EXPECTEDNESS

Expectedness will only be documented for SAEs. An SAE will be considered unexpected if the nature, severity, or frequency of the event is not consistent with the risk information previously described for the study agent.

8.3.4 TIME PERIOD AND FREQUENCY FOR EVENT ASSESSMENT AND FOLLOW-UP

The occurrence of an AE or SAE may come to the attention of study personnel during study visits and interviews of a study participant presenting for medical care, or upon review by a study monitor. All study intervention-related AEs including local and systemic reactions not meeting the criteria for SAEs will be captured on the appropriate CRF. Information to be collected includes event description, date of onset, clinician's assessment of severity, relationship to study product (assessed only by those with the training and authority to make a diagnosis), and date of resolution/stabilization of the event. All study drug or intervention-related AEs and SAEs, as well as unrelated SAEs occurring while on study must be documented appropriately. All study intervention-related AEs and SAEs, as well as unrelated SAEs will be followed to adequate resolution per investigator (e.g., to grade 1 or baseline) during the study treatment period for up to 2 years from Day 1. After the study treatment period of 2 years from Day 1, AEs will be managed by the treating physicians per standard of care.

Any medical condition that is present at the time the participant is screened up through the patient's first dose of study treatment will be considered as baseline medical history and will not be reported as an AE.

Changes in the severity of an AE will be documented to allow an assessment of the duration of the event at each level of severity to be performed. AEs characterized as intermittent require documentation of onset and duration of each episode.

Investigators will record all reportable events with start dates occurring any time after the first dose of study medication until 30 days after the last day of study treatment. SAEs will be followed until resolution or stabilization. At each study visit, the investigator will inquire about the occurrence of AE/ SAEs since the last visit.

8.3.5 ADVERSE EVENT REPORTING

The investigator must record related non-serious adverse events and report to DSMC and IRB according to timetable for reporting specified in section 10.1.6.

Adverse Events may be spontaneously identified by the patient and/or in response to an open question from study personnel or revealed by observation, physical examination, or other diagnostic procedures. Any clinically relevant deterioration in laboratory assessments or other clinical finding attributed as related to the study treatment or intervention is considered to be an AE. When possible, signs and symptoms indicating a common underlying pathology should be noted as one comprehensive event.

All Adverse Events which are serious must be reported per section 8.3.6 to Takeda Pharmacovigilance (or designee), sponsor-investigator, and the University of Colorado DSMC from the first dose of brigatinib up to and including 30 days after administration of the last dose of brigatinib. In addition, new primary malignancies that occur during the follow-up periods must be reported, regardless of causality to study regimen, for a minimum of three years after the last dose of the investigational product, starting from the first dose of study drug. All new cases of primary malignancy must be reported to Takeda Pharmacovigilance (or designee).

Planned hospital admissions or surgical procedures for an illness or disease that existed before the patient was enrolled in the trial are not to be considered AEs unless the condition deteriorated in an unexpected manner during the trial and the attribution is determined to be related to the study intervention (e.g., surgery was performed earlier or later than planned). All SAEs should be monitored until they are resolved or are clearly determined to be due to a patient's stable or chronic condition or intercurrent illness (es).

Since this is an investigator-initiated study, the principal investigator [name], also referred to as the sponsor-investigator, is responsible for reporting serious adverse events (SAEs) to any regulatory agency and to the sponsor- investigator's EC or IRB.

Regardless of expectedness or causality, all events meeting SAE criteria must be reported in English to Takeda Pharmacovigilance or designee, to the sponsor-investigator, and to the University of Colorado DSMC (see additional SAE reporting instructions in section 8.3.6):

Fatal and Life-Threatening SAEs within 24 hours of the sponsor-investigator's observation or awareness of the event

All other serious (non-fatal/non life threatening) events within 24 hours of the sponsor-investigator's observation or awareness of the event

US and Canada

Toll-Free [contact]

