Grade 1	Withhold the dose until pneumonitis returns to grade 0 (baseline), then resume at 90 mg and do not escalate. If pneumonitis recurs, permanently discontinue treatment.*
Grade 2	Withhold the dose until pneumonitis returns to Grade 0, then resume at 60 mg and do not escalate.* If pneumonitis recurs, permanently discontinue treatment.*
Grade 3	Permanently discontinue treatment.*
Grade 4	Permanently discontinue treatment.*

*Or in select cases per investigator discretion and discussion with Lead PI, consider continued use/shallower dose escalation as per Camidge et al, JTO 2019

BRIGATINIB DOSE MODIFICATION RECOMMENDATIONS FOR TREATMENT-RELATED PNEUMONITIS OCCURRING AFTER DOSE ESCALATION TO 180 MG QD:

Toxicity Grade (CTCAE v4.03)	Recommended Action
Grade 1	Withhold the dose until pneumonitis returns to grade 0 (baseline), then resume at the same dose. If pneumonitis recurs, permanently discontinue treatment.*
Grade 2	Withhold the dose until pneumonitis returns to Grade 0. Resume at 120 mg QD.* If pneumonitis recurs, permanently discontinue treatment.*
Grade 3	Permanently discontinue treatment.*
Grade 4	Permanently discontinue treatment.*

*Or in select cases per investigator discretion and discussion with Lead PI, consider continued use/shallower dose escalation as per Camidge et al, JTO 2019

6.1.2.3 DOSE MODIFICATION RECOMMENDATION TABLE FOR TREATMENT-RELATED ADVERSE EVENTS (EXCLUDING PNEUMONITIS)

Table 2: Brigatinib Dose Modification Recommendations for Treatment-Related Adverse Events (excluding pneumonitis)

Adverse Reaction	Severity*	Dose Modification
Hypertension	Grade 3 hypertension (SBP greater than or equal to 160 mmHg or DBP greater than or equal to 100 mmHg, medical intervention indicated, more than one anti-hypertensive drug, or more intensive therapy than previously used indicated)	
Withhold brigatinib until hypertension has recovered to Grade 1 or less (SBP less than 140 mmHg and DBP less than 90 mmHg), then resume brigatinib at same dose.Recurrence: withhold brigatinib until recovery to Grade 1 or less, and resume at next lower dose (Table 1) or permanently discontinue treatment.

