9.4.7 TABULATION OF INDIVIDUAL PARTICIPANT DATA

Listings will be created from all study data, grouped by domain (e.g. demographics, adverse events, lab values, outcome data, etc.).

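### Optional: section 9.4.4 counts laboratory toxicity only when the investigator calls it an AE; add a worst-grade laboratory table from values already collected

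*Combined protocol and SAP*

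**What the plan says.** **What counts as an AE.** Section 8.3.1 builds causality into the definition: an AE is an "untoward or unfavorable medical occurrence considered to be related to a study intervention or treatment in humans". Section 8.3.3.2 adds: "Only adverse events directly related to study treatment or procedures will be recorded". For laboratory results, section 8.3.5 sets two conditions, relevance and attribution: "Any clinically relevant deterioration in laboratory assessments or other clinical finding attributed as related to the study treatment or intervention is considered to be an" adverse event. No section defines clinical relevance.

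**How relatedness is decided.** Section 8.3.3.2 defines Related broadly. It ends with a bare timing criterion: "or there is a temporal relationship between the study procedure and event". If there is any doubt, the event is to be reported as related. Not Related applies if "there is no temporal relationship between the study procedure and event onset, or an alternate etiology has been established". SAEs are reported whatever their cause (8.3.3.2, 8.3.5).

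**What is analysed.** Under section 9.4.4, "the rate and type of adverse event (AE) will be compared to historical controls and assessed for any increased risk". That section also plans listings of study-related AEs. The historical controls are not identified.

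**What happens to the laboratory values.** The Schedule of Events (1.3) has CBC, CMP, CPK, lipase and amylase at screening and at every visit through week 104 or termination. Section 10.1.7.1 has laboratory data entered in REDCap. The one planned output that names laboratory values is in section 9.4.7: "Listings will be created from all study data, grouped by domain (e.g. demographics, adverse events, lab values, outcome data, etc". Section 9.4.1 promises descriptive summaries in general terms and defines the safety data set as everyone who receives at least one dose. No section plans a graded laboratory table.

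**The concern.** A Grade 3-4 laboratory result is a number compared with a threshold. Under this plan, a non-serious one reaches the toxicity rate only after two judgements, relevance and relatedness, made in an unblinded single-arm trial at three sites. Two investigators could look at the same value and classify it differently. The resulting rate is then set against historical controls whose own method of counting laboratory toxicity is not stated.

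Short-term safety is part of the trial's stated goal (9.2). A rate that does not depend on attribution could be computed from data the trial already holds, but no such table is promised. What is at stake is the reproducibility of the laboratory toxicity rate, not the efficacy conclusion.

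**Working it through.** **1. The plan's own figure.** The only design calculation is the power in 9.2. With 19 patients and rejection at 16 or more successes, P(X ≥ 16 | p = 0.60) = 0.0230 and P(X ≥ 16 | p = 0.90) = 0.8850. This matches the stated 88.5%. Nothing below depends on it.

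**2. Which Grade 3-4 laboratory values reach the 9.4.4 rate.** Reading sections 8.3.1 to 8.3.5 together:

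| Grade 3-4 value | Rule | In the AE rate? |
|---|---|---|
| Non-serious, judged relevant; related, doubtful or linked in time | 8.3.3.2, 8.3.5 | Yes |
| Serious and related | 8.3.2, 8.3.5 | Yes |
| Serious and unrelated | Reported under 8.3.3.2 and 8.3.5 | Not stated in 9.4.4; the 8.3.1 definition would leave it out |
| Non-serious, judged not clinically relevant | 8.3.5 | No |
| Non-serious, alternate cause established | Not Related in 8.3.3.2 | No |

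The last two rows are the gap.

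- *Relevance route.* The rule on doubtful cases concerns relatedness only, so it does not reach a value set aside as not relevant.
- *Other-cause route.* This is narrower. Any value drawn on treatment is linked in time, which points to Related. An established other cause points to Not Related. Section 8.3.3.2 does not say which prevails, but doubt resolves to related, so only a confident attribution elsewhere removes the event. Such attributions are possible here: ALT/AST up to 5 × ULN is allowed at entry with liver metastases (5.1), no washout of prior therapy is required (5.2), and conditions present up to the first dose are baseline history (8.3.4).

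**3. Scale.** The documents give no laboratory toxicity rate and no misclassification rate, so the size cannot be estimated. Only the weight of one patient can be shown. Inputs are 23 planned enrolled patients (9.2, 9.4.6), with 19 and 35 as the synopsis minimum and maximum. The number actually treated is not fixed in advance.

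Change per uncounted patient = 1/n:

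- n = 19: 1/19 = 5.3 points
- n = 23: 1/23 = 4.3 points
- n = 35: 1/35 = 2.9 points

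Exact (Clopper-Pearson) 95% limits for x of n are: lower = Beta quantile 0.025 with parameters (x, n − x + 1); upper = Beta quantile 0.975 with parameters (x + 1, n − x). For x = 0 the lower limit is 0 and the upper limit is 1 − 0.025^(1/n). For one laboratory term at n = 23:

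| Patients counted | Proportion | Exact 95% CI |
|---|---|---|
| 0 | 0% | 0 to 1 − 0.025^(1/23) = 14.8% |
| 1 | 1/23 = 4.3% | 0.1% to 21.9% |
| 2 | 2/23 = 8.7% | 1.1% to 28.0% |

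The range of 0 to 2 missed patients is an assumption chosen for illustration. The intervals overlap widely.

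**The case against.** **The strongest case against.** Restricting AEs to related events is a consistent design choice for an approved drug given at its approved dose. A toxicity rate that leaves out a change with an established other cause does what it was meant to do. The safeguards are real: doubt and timing both push towards related, SAEs are reported whatever the cause, events may be picked up on monitor review (8.3.4), and the DSMC receives toxicity and dose-modification summaries (10.1.4). The values stay in REDCap and are listed, so a graded table could be produced at any time. Section 9.4.1's descriptive statistics, or the CTCAE reference in 9.4.4, might be read as covering one already.

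**What of it stands.** Most of it. The safeguards nearly close the relatedness route, and no data are lost. They do not close the relevance route, and the general lines in 9.4.1 and 9.4.4 commit to no graded laboratory table: the quantity named for analysis is the AE rate.

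**Stronger readings that the documents do not support.**

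- *The toxicity rate is biased low against the controls.* The controls and their counting rule are unspecified. If they counted related AEs only, the planned rate already matches them, so no direction of bias can be stated.
- *Liver tests and blood counts are especially exposed because Table 2 (6.1.2.3) gives them no row of their own.* One title governs every row of that table: "Brigatinib Dose Modification Recommendations for Treatment-Related Adverse Events (excluding pneumonitis". The CPK, lipase and amylase rows presuppose attribution just as the catch-all row does.
- *Asymptomatic laboratory abnormalities may be left out of AE counting.* The footnote that a reader might cite belongs to the dose-modification table and calls for discussion with the lead PI. It is not a rule for counting AEs.

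**Conclusion.** The point holds as an optional, inexpensive improvement, not as an error. The laboratory part of the 9.4.4 rate depends on investigator judgement. The remaining gap is mainly non-serious Grade 3-4 values judged not clinically relevant or given an established other cause.

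The size is unknown and may be zero. With 23 treated, each uncounted patient is worth 4.3 points (5.3 at 19, 2.9 at 35). The primary endpoint, its test and the sample size are unaffected.

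Two assumptions apply. The number of missed patients is illustrative. That the CMP includes ALT, AST and bilirubin is its usual content, but the documents do not list its components.

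**What to change.** Add to section 9.4.4 wording such as:

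> For the safety data set, each patient's worst CTCAE v4.03 grade from first dose to 30 days after last dose will be derived from the collected values of the scheduled laboratory tests (CBC, CMP, CPK, lipase, amylase; tests with a numeric CTCAE grade), regardless of attribution. Results will be tabulated as a shift from baseline grade (last value before first dose), with the Grade 3-4 proportion and exact 95% CI, beside the investigator-reported AEs. Any comparison with historical controls will use whichever measure, laboratory-derived or investigator-reported, matches how the control rate was defined.

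The 30-day limit follows the AE window in 8.3.4.

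**Cost.** One paragraph of analysis text and a few tables from data already in REDCap. No new tests, visits or staff are needed.

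**Downside.** A count that ignores attribution includes changes caused by disease or prior therapy, and it may look less favourable. The shift from baseline helps with abnormalities present at entry. The table should be read with the AE table and should not replace it.
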